## 20 APPENDIX 2 PROTOCOL DEFINED PULMONARY EXACERBATION DEFINITION

The presence of a pulmonary exacerbation is established by the following:

- (1) One of the major criteria alone  
or
- (2) Two of the minor signs/symptoms and fulfillment of symptom duration

**Major Criteria:** *(One finding alone establishes the presence of a pulmonary exacerbation)*

- (1) Absolute decrease in FEV1 %predicted of  $\geq 10\%$
- (2) Oxygen saturation  $< 90\%$  on room air *or* absolute decrease of  $\geq 5\%$
- (3) New lobar infiltrate(s) or atelectasi(e)s on chest radiograph
- (4) Hemoptysis (more than streaks on more than one occasion in past week)

**Minor Signs/Symptoms:** *(Two minor signs/symptoms are required in the absence of major criteria. If at least 2 minor signs/symptoms are present, at least one needs to be 3 or more days in duration to meet the pulmonary exacerbation definition)*

- (1) Increased work of breathing or respiratory rate
- (2) New or increased adventitial sounds on lung exam
- (3) Weight loss  $\geq 5\%$  of body weight or decrease across 1 major percentile in weight percentile for age in past 6 months
- (4) Increased cough
- (5) Decreased exercise tolerance or level of activity
- (6) Increased chest congestion or change in sputum

1.1 Study Rationale and Design

Patients with cystic fibrosis (CF) commonly acquire a chronic airway infection with *Pseudomonas aeruginosa* (*P.a.*). Both inhaled tobramycin and oral azithromycin have been proven beneficial in these patients and are currently used by the majority of eligible patients. Seventy five percent of US patients prescribed inhaled tobramycin are also prescribed chronic oral azithromycin. We believe that azithromycin is inhibiting the anti-*P.a.* effects and clinical benefits of inhaled tobramycin. This study will investigate whether azithromycin is associated with poorer clinical and microbiologic outcomes as compared to placebo during concurrent administration of inhaled tobramycin.

This is a prospective, randomized, placebo-controlled, double-blinded study of azithromycin in subjects with chronic *Pa* airway infection using inhaled tobramycin. Subjects who have received two (2) or more cycles of inhaled tobramycin within the 24 weeks prior to enrollment will be recruited into the study. Approximately 120 eligible subjects (allowing for 10 withdrawn) will be enrolled and randomized to either azithromycin or placebo at Visit 1 (Day -14), approximately 14 days prior to the start day of their next planned 28-day nebulized solution or dry powder tobramycin (TISP) cycle. Subjects will be randomized in a 1:1 fashion to azithromycin (500 mg three times per week) or matched placebo.

Between Visit 1 (Day -14) and Visit 2 (Day 0), a two-week run-in period will be used to begin administration of either azithromycin or placebo. Among those randomized to azithromycin, the 2-week run-in period will be used to initiate azithromycin and standardize uptake prior to the start of the next TISP cycle. Among those randomized to placebo, the run-in period will be used as a standardized washout prior to the start of the next TISP cycle. Subjects will begin TISP at Visit 2 in addition to their continued dosing of randomized study drug treatment (azithromycin or placebo). Subjects will continue both TISP and study drug dosing for 28 days (up until Visit 3), which corresponds with the end of a clinically prescribed 4-week cycle of TISP. Subjects completing the study through Visit 3 (Day 28) will be offered participation and consent to an 8-week open-label extension period during which azithromycin will be provided. During the open-label period, subjects will be instructed to remain off of TISP for the first 4-week period, followed by a 4-week period of TISP. Total duration of subject participation will be up to 6 weeks for those enrolled in the randomized study and up to 98 days for subjects participating in the optional open-label extension. Subjects who meet all inclusion criteria and none of the exclusion criteria will be eligible for the study.

The primary objective of this study is to determine if azithromycin impairs the previously-recognized clinical benefits of inhaled tobramycin by comparing changes in pulmonary function as measured by FEV₁ between subjects randomized to azithromycin versus placebo.

The secondary objectives for the randomized period are to:

- Compare changes in patient-reported quality of life between subjects randomized to azithromycin versus placebo

The secondary exploratory objectives for the randomized period are to:

- Compare the safety profile between subjects randomized to azithromycin versus placebo
- Compare changes in additional spirometry measures, bacterial density, and weight between subjects randomized to azithromycin versus placebo
- Compare rates of pulmonary exacerbations, hospitalizations, and acute antibiotic usage between subjects randomized to azithromycin versus placebo

The objectives for those continuing in the open-label extension:

- Among those randomized to azithromycin and remaining on azithromycin, obtain additional data to determine the long term effect of azithromycin on clinical outcomes
- Among those randomized to placebo and switching to azithromycin, compare differences in clinical outcomes observed during the randomized and open label periods

1.2 Interim Data Safety Monitoring Board Reviews

Safety monitoring and study conduct will be assessed by a DSMB with members appointed by the NHLBI. The DSMB is responsible for safeguarding the interests of study participants, assessing the safety and efficacy of study procedures and for monitoring overall study conduct. Serious adverse events (SAEs) will be monitored on an ongoing basis. In addition to SAE monitoring, quarterly summary reports tabulating SAEs by treatment group will be provided to the DSMB. A comprehensive interim report will be provided to the DSMB when approximately 50% of patients have completed the randomized portion of the trial. The report will include an overview of enrollment by site, detailed summaries of all SAEs, AEs, withdrawals, drug discontinuations, hospitalizations, protocol violations and other clinical safety endpoints. Table shells detailing the results to be presented in the semi-annual reports are included in Appendix A (randomized period) and Appendix B (open-label period), whereas Appendix C will include listings of protocol violations and SAE narratives.

1.3 Statistical Monitoring Guidelines and Stopping Rules

While there are no pre-determined stopping rules for safety, the DSMB may decide to stop the study either temporarily or permanently if there are significant concerns regarding subject safety. There is however pre-specified stopping rule for efficacy/harm and futility with respect to the primary endpoint.

Should the DSMB consider stopping the trial based on the primary endpoint, they will be guided by a formal stopping rule to be assessed when approximately 50% of patients have completed the randomized portion of the trial. The primary endpoint is the difference between the azithromycin and placebo treatment groups in the relative change in FEV₁ (liters) from randomization at Visit 1 (Day -14) to Visit 3 (Day 28). We hypothesize that azithromycin is associated with poorer clinical outcomes (inferiority) as compared to placebo during concurrent administration of inhaled tobramycin and thus there will be a smaller improvement or a worsening in FEV₁ in the azithromycin treatment group as compared to placebo treatment from Visit 1 (Day -14) to Visit 3 (Day 28). Assuming a sample size of 110 subjects, two-sided type 1 error of 0.05, and a standard deviation for the relative change of 13%, the study has approximately 85% power to detect a difference (relative change in FEV₁ in the azithromycin treatment group minus the relative change in FEV₁ in the placebo treatment group) of less than or equal to -7.5% (e.g. azithromycin is clinically inferior to placebo).

For the purposes of calculating formal boundaries for stopping under the null and alternative hypotheses (no difference, and clinical inferiority of azithromycin, respectively), we will use the hypothesized treatment effect of -7.5%. Assuming a conservative O'Brien-Fleming boundary¹, the two-sided stopping rule would suggest that the trial be stopped early in favor of the alternative hypothesis (azithromycin inferiority) if the observed treatment effect is less than -9.8% at the interim review (n=55). Should there be evidence in the opposite direction where azithromycin is clinically superior to placebo, the trial will be stopped at the interim analysis when observed treatment effect is 9.8% or greater. The trial *could* stop under the null hypothesis if the observed treatment effect is greater than 0.05% but less than 9.8% *and the DSMB has simultaneous safety or accrual concerns*. If the trial was to continue to completion, the null hypothesis will be rejected in favor of the alternative if the observed treatment effect is less than or equal to -4.9% at the end of the trial.

The probability of stopping at the interim analysis if the true treatment effect is 0.0% is 0.016 (or less than 2%). Similarly, if the treatment effect is $\pm 3.75\%$ or $\pm 7.5\%$ the probability of stopping is 0.05 and 0.26, respectively.

The actual stopping boundaries will be computed at the time of the comprehensive interim report to the DSMB. Thus, the actual stopping boundaries may differ from those provided above depending on the number of subjects evaluable for the primary endpoint. R RCTdesign software will be used to calculate the formal stopping boundary and adjust for this interim analysis in the final analysis.

2 Report Generation

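### SAP 1.3: the printed interim stopping probabilities (0.016, 0.05, 0.26) do not follow from the printed null-stopping region (0.05% to 9.8%)

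*SAP*

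**What the plan says.** SAP 1.3 sets up the design as follows: "Assuming a sample size of 110 subjects, two-sided type 1 error of 0.05, and a standard deviation for the relative change of 13" (per cent), with a hypothesized effect of -7.5%. The boundaries are of O'Brien-Fleming type, with one formal assessment when about half the patients have completed the randomized period. The section describes them as "formal boundaries for stopping under the null and alternative hypotheses (no difference, and clinical inferiority of azithromycin, respectively").

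- **Inferiority stop:** if "the observed treatment effect is less than -9.8% at the interim review (n=55").
- **Superiority stop:** at an observed effect of 9.8% or more.
- **Null stop:** the trial could "stop under the null hypothesis if the observed treatment effect is greater than 0.05% but less than 9.8" (per cent), on the further condition that "the DSMB has simultaneous safety or accrual concerns".
- **End of trial:** the null hypothesis is rejected in favour of inferiority at -4.9% or below.

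The next paragraph gives the operating characteristics. "The probability of stopping at the interim analysis if the true treatment effect is 0.0% is 0.016", which the SAP glosses as under 2%. For ±3.75% and ±7.5%, "the probability of stopping is 0.05 and 0.26, respectively". It does not say whether these figures count the null region.

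The SAP also notes that "the actual stopping boundaries may differ from those provided above depending on the number of subjects evaluable for the primary endpoint". Protocol 14 and 15.5 place the stopping rules for futility and for efficacy/harm in the DSMB charter, which is not among the documents.

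**The concern.** Two features of the paragraph do not fit together.

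First, the written null region runs from just above zero to 9.8%. If the true effect is zero, close to half of all interim estimates fall there, yet the stated chance of stopping is below 2%.

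Second, the region lies on one side of zero. Its probability must therefore differ between a positive and a negative true effect of the same size. The SAP prints a single value for each ± pair.

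A DSMB member needs to know whether an interim estimate of, say, +1% meets the null-stopping criterion, as the text says, or means continue, as the probabilities imply. That should be settled before unblinded results are in front of the board.

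**Working it through.** **Inputs (SAP 1.3; 1:1 allocation from SAP 1.1).** Total n = 110, interim n = 55, SD 13%, two-sided alpha 0.05, one formal interim look at half information. The interim estimate is treated as normal.

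**Step 1: reproduce the design.**

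- SE at the interim: 13 × √(4/55) = 3.506%
- SE at the end: 13 × √(4/110) = 2.479%
- Two-look O'Brien-Fleming constant at two-sided 0.05: 1.977, so the critical Z values are 1.977 × √2 = 2.797 and 1.977
- Interim bound: 2.797 × 3.506 = 9.80%
- Final bound: 1.977 × 2.479 = 4.90%
- Group-sequential power at -7.5%: 0.854

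These agree with the SAP's ±9.8%, -4.9% and approximately 85%, so the model is the SAP's own.

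**Step 2: stopping probabilities.** For a true effect d and s = 3.506:

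- Outer bounds: Φ((-9.8 - d)/s) + 1 - Φ((9.8 - d)/s)
- Written null region: Φ((9.8 - d)/s) - Φ((0.05 - d)/s)
- Symmetric band: Φ((0.05 - d)/s) - Φ((-0.05 - d)/s)

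Example at d = 0: 9.8/3.506 = 2.795 and 0.05/3.506 = 0.0143. The outer bounds give 2 × 0.0026 = 0.0052, and the written region gives 0.9974 - 0.5057 = 0.4917.

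| True effect | SAP prints | Outer bounds | Written region | Outer + written region | Band ±0.05% | Outer + band |
|---|---|---|---|---|---|---|
| 0 | 0.016 | 0.0052 | 0.4917 | 0.497 | 0.0114 | 0.0166 |
| -3.75% | 0.05 | 0.0423 | 0.1391 | 0.181 | 0.0064 | 0.0487 |
| +3.75% | 0.05 | 0.0423 | 0.8122 | 0.854 | 0.0064 | 0.0487 |
| -7.5% | 0.26 | 0.2559 | 0.0156 | 0.272 | 0.0012 | 0.2571 |
| +7.5% | 0.26 | 0.2559 | 0.7273 | 0.983 | 0.0012 | 0.2571 |

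The column for outer bounds plus the written region is an upper limit, because it assumes the DSMB always acts on that region.

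Only the last column is close to all the printed values. A band half-width between 0.0453% and 0.0497% rounds to 0.016 at d = 0; exactly 0.05% rounds to 0.017. That such a band lies behind the figures is inferred from the numbers.

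**Step 3: alternative explanations.**

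- *Occasional use of the written region.* The rate that gives 0.016 at zero is (0.016 - 0.0052)/0.4917 = 0.022. The same rate gives 0.045 and 0.256 at -3.75% and -7.5%, but 0.060 and 0.272 at +3.75% and +7.5%.
- *Rounding of the bound.* Bounds of 9.75% to 9.85% give 0.0054 to 0.0050 at zero.
- *A t distribution with 53 df.* The outer bounds give 0.007 at zero.
- *Boundaries recomputed at the interim.* With 50, 55 or 60 evaluable subjects the bounds are 10.28%, 9.80% and 9.39%. At zero, the outer bounds give 0.005 each time, and adding the written region gives 0.497 each time.

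**Step 4: effect on the inferiority test.** Integrating over the interim estimate, power at -7.5% is 0.854 without the null clause and 0.852 with it always enforced. Type I error in the inferiority direction is 0.0250 and 0.0247.

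**The case against.** The best defence is that the null stop is optional. It applies only when the DSMB also has safety or accrual concerns, so the probabilities may describe the formal boundaries, with the clause laid on top. On that view 0.497, 0.854 and 0.983 are ceilings that would not be reached, and the true stopping probability cannot be calculated because no document gives the chance of such concerns. The direction of the region is also coherent: when the alternative is azithromycin inferiority, a positive interim estimate is a natural trigger for futility. If the clause were used about 2.2% of the time, the figures on the hypothesized, negative side would agree with print after rounding. The design itself reproduces, the boundaries will be recomputed, and the charter may already be clear.

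Much of this stands. The high values are upper limits, the clause costs almost no power, and the charter could not be checked. The documents also do not say whether the interim review is still ahead.

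The defence does not rescue the printed probabilities. If the optional clause was left out, the value at zero should be 0.005, about a third of 0.016, and the value at ±3.75% should round to 0.04. If it was used at a low constant rate, the positive side gives 0.060 and 0.272, not 0.05 and 0.26. A rate that varied with the true effect could be chosen to fit, but the SAP states none.

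**Conclusion.** The concern holds. The SAP's written null-stopping region and its stated stopping probabilities describe different rules. Under no effect, the printed 0.016 compares with 0.005 for the outer bounds alone and with at most 0.497 once the written region is counted. The single value for each ± pair is not what a region on one side of zero produces.

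This rests on the SAP's inputs (n = 55 of 110, SD 13%, 1:1 allocation, one look), a normal model, and a constant rate of use for the optional clause. The documents do not show which of the two statements is the intended one.

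The consequence is limited. The outer bounds, final bound and 85% power are sound, and always enforcing the clause would lower power at -7.5% by about 0.003 (0.8541 to 0.8516) without inflating the type I error. What is wrong is the guidance to the DSMB, and it should be fixed.

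**What to change.** Before the interim review, or as a documented clarification if it has already taken place, the sponsor's statistician and the DSMB should state which rule is intended and make SAP 1.3 and the DSMB charter agree.

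- **If futility in the inferiority direction is intended (the more useful option):** keep the region 0.05% to 9.8% and say that the null stop is non-binding. Replace the probabilities with two labelled sets. The first is for the outer bounds only: 0.005 at 0, 0.042 at ±3.75% and 0.256 at ±7.5%. The second gives upper limits including the null region: 0.497 at 0, 0.181 and 0.854 at -3.75% and +3.75%, and 0.272 and 0.983 at -7.5% and +7.5%.
- **If the probabilities are right:** print the null region as -0.05% to +0.05% and call the rest, out to ±9.8%, continuation. At exactly 0.05%, 0.016 becomes 0.017. The drawback is that a null stop then has only about a 1.1% chance under no effect, so there is almost no futility stopping.

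In either case, say which null region will be used when the boundaries are recomputed. The cost is a sentence or a few numbers in SAP 1.3 and the matching charter text. No patients or data are needed, and the outer bounds, final bound and sample size do not change.

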### 15.1 Data Sets Analyzed

All analyses will be performed using a modified intent-to-treat (m-ITT) population, which is defined as all randomized subjects who received at least one dose of study drug. Subjects who are discontinued from study drug temporarily or permanently are encouraged to complete all remaining study visits and will remain in the analyses population according to ITT. The primary efficacy analyses will be repeated in the per-protocol population, which is defined as subjects having completed  $\geq 80\%$  of doses (azithromycin and or placebo) and who did not require the use of acute antibiotics or steroids. All tests will be two-sided and evaluated at a 0.05 level of significance.

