### 15.3 Analysis of Primary Endpoint

The primary endpoint will be the difference between the azithromycin and placebo treatment groups in the relative change from Visit 1 to Visit 3 in FEV1 (liters). The primary endpoint will be compared between treatment groups using linear regression adjusted for randomization strata. Least squares means and the treatment effect for the relative change will be presented as well as corresponding 95% confidence interval and p-values. The p-values will be evaluated against a two-sided 0.05 level of significance.

Additional secondary analysis may be performed to adjust for potential baseline confounders including age, sex, and baseline FEV1. Sensitivity analyses of the primary endpoint will be performed using the per-protocol population. Additional sensitivity analyses will be performed to address missing data. Specifically, the least favorable treatment arm imputation method will be used which imputes that missing value with the mean change from the treatment arm with the worst change in the observed case analysis. Further details regarding the handling of missing data will be provided in the statistical analysis plan.

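### The interim null-stop zone in SAP 1.3 reaches up to the azithromycin-superiority bound and contradicts the SAP's own stopping probabilities, and the final rule omits the upper bound that the two-sided design implies

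*SAP*

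**What the plan says.** The primary test is two-sided throughout. Protocol 15.1 states "All tests will be two-sided and evaluated at a 0.05 level of significance", and Protocol 15.3 says of the primary endpoint "The p-values will be evaluated against a two-sided 0.05 level of significance". The design statement in SAP 1.3 begins "Assuming a sample size of 110 subjects, two-sided type 1 error of 0.05, and a standard deviation for the relative change of 13" percent, and goes on that "the study has approximately 85% power to detect a difference" of -7.5% or beyond. SAP 1.3 also calls the stopping rule itself two-sided.

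For the boundaries, SAP 1.3 says "we will use the hypothesized treatment effect of -7.5" percent, names no difference as the null and clinical inferiority of azithromycin as the alternative, and uses an O'Brien-Fleming shape. The rules are then:

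- **Interim, harm:** stop below -9.8% (n = 55).
- **Interim, benefit:** "the trial will be stopped at the interim analysis when observed treatment effect is 9.8% or greater".
- **Interim, null:** the trial could "stop under the null hypothesis if the observed treatment effect is greater than 0.05% but less than 9.8" percent, if the DSMB has safety or accrual concerns at the same time.
- **Final:** "the null hypothesis will be rejected in favor of the alternative if the observed treatment effect is less than or equal to -4.9" percent. No positive counterpart is printed.

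The same section gives the probability of stopping at the interim as 0.016 at a true effect of zero, 0.05 at ±3.75% and 0.26 at ±7.5%. SAP A.5 says that the primary analysis, with its confidence interval and p-value, is adjusted for the sequential monitoring.

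**The concern.** The null-stop zone lies wholly on the azithromycin-better side and ends where the superiority stop begins. Its upper part is evidence against no difference, so a stop there cannot sensibly be called a stop under that hypothesis. A zone of this shape would suit a futility statement that inferiority can no longer be shown, but the text does not say that.

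The printed rule also has two directions at the interim and one at the end. A final estimate of +6% (z = 6/2.479 = 2.42, p = 0.016) meets no printed rejection rule, while the two-sided test in Protocol 15.3 would reject. The reading of such a result should not be left to be settled after the data are seen.

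The direction matters. Protocol 2.1 accepts that removing azithromycin may lower lung function, although it adds that the preliminary data do not support this concern. The trial could therefore end on either side of zero, and the result is meant to inform whether two widely used drugs are combined.

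**Working it through.** **Inputs.** SD 13, 110 subjects at the end and 55 at the interim, two-sided alpha 0.05, design effect -7.5% (SAP 1.3); 1:1 allocation (Protocol 8.1). I assume one interim look at half the information, as SAP 1.3 describes, with 27.5 subjects per arm.

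**Step 1. Reproduce the plan's figures.**

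- SE at the interim = 13 × √(2/27.5) = 3.506. SE at the end = 13 × √(2/55) = 2.479.
- A two-look, two-sided O'Brien-Fleming design at alpha 0.05 has critical value c = 1.977 at the end and c × √2 = 2.797 at the interim.
- Interim bounds: ±2.797 × 3.506 = ±9.8%. Final bounds: ±1.977 × 2.479 = ±4.9%.
- Power at -7.5% is 0.854 with this design. Without the interim look it is 0.857 by the normal formula and 0.850 by the noncentral t.

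The printed ±9.8%, -4.9% and 85% all reproduce. A one-sided 0.025 design with a binding null stop at zero gives -9.78% and -4.89%, which round to the same harm bounds. The bounds alone therefore do not settle sidedness; the stated two-sided test does.

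**Step 2. Interim results inside the null-stop zone.**

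- +7%: z = 7/3.506 = 2.00, nominal two-sided p = 0.046.
- +9.7%: z = 9.7/3.506 = 2.77, p = 0.006.
- If the present trend continues, the chance of ending at or above +4.9% is Φ((2x - 9.8)/3.506) for an interim estimate x. This is 50% at +4.9% and 88% at +7%.
- At a true +7.5% the interim estimate falls in the zone with probability Φ((9.8 - 7.5)/3.506) - Φ((0.05 - 7.5)/3.506) = 0.73. This is the chance of entering the zone, not of stopping.

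**Step 3. Compare with the SAP's stopping probabilities.** For a true effect θ, the outer bounds contribute Φ((-9.8 - θ)/3.506) + 1 - Φ((9.8 - θ)/3.506). A null zone from a to b adds Φ((b - θ)/3.506) - Φ((a - θ)/3.506).

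| True effect | SAP 1.3 states | Outer bounds only | Plus a band of ±0.05% | Plus every entry to +0.05% to +9.8% |
|---|---|---|---|---|
| 0 | 0.016 | 0.005 | 0.017 | 0.50 |
| +3.75% | 0.05 | 0.042 | 0.049 | 0.85 |
| -3.75% | 0.05 | 0.042 | 0.049 | 0.18 |
| +7.5% | 0.26 | 0.256 | 0.257 | 0.98 |
| -7.5% | 0.26 | 0.256 | 0.257 | 0.27 |

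Only the narrow band comes close at all three effect sizes; an unrounded half-width of 0.045% to 0.05% gives 0.015 to 0.017 at zero. The printed zone would also give different values for plus and minus the same effect, whereas the SAP gives one value for both.

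**Step 4. Effect of the missing final bound, with no null stop taken.**

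- Under no effect, each interim bound is crossed with probability 0.0026 and each final bound, after continuing, with 0.0225.
- Both final bounds: 2 × (0.0026 + 0.0225) = 0.050.
- As printed: 0.0026 + 0.0026 + 0.0225 = 0.028.
- Chance of declaring benefit at a true +7.5%: 0.256 at the interim plus 0.598 at the end = 0.854 with both bounds; 0.256 as printed.

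**The case against.** A reader might infer that the trial stops whenever azithromycin looks slightly better, that the final test is one-sided, and that a real benefit would be closed out as no difference. The documents do not support that reading.

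- The null stop is optional and needs concurrent DSMB concerns about safety or accrual. SAP 1.3 already allows a safety stop at any time, so part of what the clause permits exists without it.
- The -4.9% sentence says when the null is rejected for inferiority. It does not say that superiority cannot be declared. Protocol 15.3 and SAP A.5 still give a two-sided p-value, with the SAP adjusting for monitoring, and the interim rule declares superiority at +9.8%.
- Nothing says that a stop in the zone is reported as no difference. SAP 1.3 introduces this part of the rule as futility.
- Protocol 14 and 15.5 place the stopping rules in the DSMB charter, which is not available here, and SAP 1.3 says the bounds will be recomputed at the interim.

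All of this stands, and it limits the consequences. It does not remove the two defects. The extra condition governs when the zone may be used; it does not turn p = 0.006 into support for the null. Nor does leaving the optional stop out of the calculation rescue the SAP's figures: the outer bounds alone give 0.005 at zero, not 0.016. Recomputing bounds at the interim does not supply a direction that the rule never states.

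**Conclusion.** The rule is wrong as written in two places, both within SAP 1.3.

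1. The null-stop zone of +0.05% to +9.8% conflicts with the null it is attached to and with the stopping probabilities given in the same section. The figures fit a band of about ±0.05% around zero. That such a band was intended is an inference from the arithmetic; no document says so.
2. The upper final bound of +4.9%, which the stated two-sided O'Brien-Fleming design implies, is not printed. This is an omission that conflicts with the two-sided test, not an explicit one-sided test.

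The figures of 0.028 and 26%, against 0.05 and 85%, describe the literal boundary rule only. They do not describe what the planned two-sided adjusted p-value could show. All results rest on SD 13, 55 and 110 evaluable subjects, and one interim look at half the information.

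**What to change.** In SAP 1.3 and the DSMB charter:

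1. State the final rejection rule in both directions: at or below -4.9%, or at or above +4.9%, at the planning values.
2. Reconcile the null-stop zone with the stated stopping probabilities, so that it no longer runs up to the superiority bound. If a one-directional futility zone is what is wanted, label it as inferiority that cannot be shown, and recompute the stopping probabilities to include it.
3. State that any stop in the zone is reported with the sequentially adjusted two-sided estimate, confidence interval and p-value.

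No particular conditional-power cap is needed. The cost is wording and, under the second option, one recalculation. No extra subjects are required. With both final bounds and no null stop taken, type I error is 0.050, so narrowing an optional null stop does not push it above the stated level.
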